**Topical Nitroglycerine Treatment for Radial Artery Spasm Prevention
(TNT-RASP)**

NCT02832115

October 4 2020

Background:

Vascular access site complications (VASC) during cardiac catheterizations are significantly higher in transfemoral access compared to transradial access. Main disadvantage in radial access is the restriction in size of catheters as well as incidence of radial artery spasm. Radial spasm is identified by pain in the forearm aggravated by movement of the catheter/sheath; difficulty in manipulating the catheter; loss of radial pulse or damping of radial arterial pressure. Tortuosity and loops in upper extremity arterial tree could mimic some findings of radial artery spasm. Incidence of radial spasm has been reported to range between 4% and 20%. Risk factors include smaller radial artery diameter, atherosclerotic lesions, entrance of guidewires into side branches, vessel tortuosity, larger arterial sheath diameters, procedure duration, female sex, younger age, lower BMI, DM, number of catheters used, volume of contrast, unsuccessful access at first attempt, fear and anxiety. Mean size of radial artery is reported at 2.44 mm. Women and persons of south Asian descent tend to have smaller radial arteries with means of 1.91mm and 2.00 mm, respectively. Outer diameters of commonly used 5F and 6F sheaths are 2.16 mm and 2.62 mm, respectively. Ratio of radial artery to sheath size affects post-procedural radial artery flow.

Intraarterial vasodilators reduce radial artery spasm. Transdermal vasodilators prior to vascular access would increase chance for successful arterial access in first attempt and increase radial artery to sheath size ratio both of which should have additive benefit to intraarterial vasodilators in reducing spasm. Transdermal lidocaine would reduce pain during s.c. lidocaine, which can further ameliorate the risk of radial artery spasm. Use of transdermal nitroglycerine has been shown to safely increase radial artery size without significant hypotension.

Aim:

To study the role of transdermal vasodilators as an adjunct to parenteral vasodilators, in reducing radial artery spasm and improving patient comfort and post procedure radial artery patency during transradial coronary angiograms and interventions.

Hypothesis:

Transdermal vasodilators will increase radial artery size and reduce radial artery spasm as well as improve patient comfort and post procedure radial artery patency.

Study Design:

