Single center, double blinded, randomized placebo-controlled study comparing effect of transdermal preparations of lidocaine + Nitroglycerine and lidocaine + placebo on radial artery spasm and procedural success in patients undergoing transradial coronary angiograms and interventions. All patients will receive standard parenteral cocktail including intraarterial or intravenous heparin and intraarterial nitroglycerine and / or verapamil. Exact doses and combinations would be at the discretion of individual provider based on patient's hemodynamic status and comorbid conditions.

End Points:

Primary:

1. Radial artery spasm: Incidence of radial artery spasm indicated by a Radial artery spasm score of 1 or more. Radial artery spasm score is sum of:
 - a. Verbal or nonverbal expression of discomfort in the forearm during catheter/sheath manipulation - Absent :0; Present:1
 - b. Difficulty in manipulating the catheter- Absence :0; Present:1
 - c. Difficulty with sheath removal: Absent: 0; Present:1
 - d. Additional use of intraarterial nitroglycerine or verapamil after the initial vasodilator cocktail for suspected radial artery spasm- No:0; Yes:1.

Secondary:

1. Change in ipsilateral radial artery cross sectional area (mm²) before application of topical nitroglycerine / placebo (pre-dilation) vs. prior to arterial puncture after application of topical nitroglycerine / placebo (Post-dilation).
2. Number of patients with Procedural failure: Need to abort procedure or convert to transfemoral approach.
3. Patient forearm discomfort or pain during procedure measured using Visual analog scale 0-10, 0 being no discomfort or pain (best) and 10 being worst discomfort or pain (worst).
4. Ipsilateral radial pulse at end of procedure 0-4+, 0 indicating no palpable pulse (worst); 1 + indicating a faint, but detectable pulse; 2 + suggesting a slightly more diminished pulse than normal; 3 + is a normal pulse; and 4 + indicating a bounding pulse (best).

Safety endpoints:

1. Asymptomatic Hypotension: SBP < 90 mm Hg
2. Symptomatic Hypotension: Dizziness or lightheadedness and SBP < 100 mm Hg
3. Intractable headache unrelieved by 1gm of acetaminophen

Adverse Effects of investigational product:

1. Hypotension: SBP < 90 mm Hg requiring intervention any time after application of investigational product (IP) in Ambulatory Cardiac Unit (Same Day) until removal of IP in Cath lab

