2. Dizziness or lightheadedness requiring intervention any time after application of IP in Ambulatory Cardiac Unit (Same Day) until removal of IP in Cath lab
3. Headache requiring intervention any time after application of IP in Ambulatory Cardiac Unit (Same Day) until removal of IP in Cath lab

Complications of Radial artery catheterization:

1. Forearm hematoma > 5cm
2. Absent ipsilateral radial pulse (0) after procedure

Methods:

1. Patient enrollment:

a. Outpatient:

- i. Whenever feasible, information about the study would be provided to the patient prior to arrival in Ambulatory Cardiac Unit (Same Day) (preferably at the time of scheduling). When not feasible, patients will be contacted via phone prior to the day of procedure or approached in the Ambulatory Cardiac Unit (Same Day) unit on the day of the procedure by one of the investigators to assess interest in participation.
- ii. Patients who are interested and meet all inclusion criteria and none of the exclusion criteria will be enrolled in the trial in the Ambulatory Cardiac Unit (Same Day) on the day of their scheduled procedure. One of the participating investigators will obtain informed consent after the patient has had time to review the consent and all questions have been answered.

b. Inpatient:

- i. Hospitalized patients who are interested and meet all inclusion criteria and none of the exclusion criteria may be enrolled in the trial on or before the day of their scheduled procedure, but always prior to transfer to the Catheterization Lab. One of the participating investigators will obtain informed consent after the patient has had time to review the consent and all questions have been answered.

2. After reviewing the most current vital signs, patients without any exclusion criteria will be randomized 1:1 to control arm (40 mg Lidocaine + placebo) or study arm (40 mg lidocaine + 30 mg nitroglycerine)

3. Study drug assignment will be randomized and distributed by a delegated member of the study staff, with oversight by the PI or Sub-Is, for patients consented and enrolled in the trial at least 60 minutes prior to the procedure start time.
4. Pre-medication cross sectional image of ipsilateral radial artery (approximately 1 inch proximal to radial styloid process) will be recorded using bedside sonogram with no more than gentle pressure and site marked with a skin marker.
5. Ipsilateral wrist circumference (1 inch proximal to radial styloid process) will be documented.

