Outcomes will be analyzed by intention to treat analysis using SPSS software. Relationship between use of nitroglycerine and radial spasm will be analyzed using Pearson Chi Square test. The radial artery dimensions before and after application of the study drug or placebo will be compared using paired sample t test. Relationship between use of nitroglycerine and procedural failure will be analyzed using Pearson Chi Square test. Relationship between use of nitroglycerine and forearm discomfort or pain during procedure measured using Visual analog

scale will be analyzed using Mann Whitney test. The post procedure pulse will be analyzed using Mann Whitney test.

Privacy Protections

It is not possible to conduct this research study without access to and the use of the patients' medical record information. The researcher (s) will only obtain the minimum necessary data to achieve the goals of the research. The data collected is not sensitive in nature. In this research project access to and the use of participants PHI involves no more than minimal risk to the privacy of the individual because the investigator(s) is (are) directly involved in the care of respective subjects as part of their patient care responsibilities. Granting of a Partial Waiver of HIPAA authorization for recruitment purposes will not adversely affect the privacy of the involved patients or the confidentiality of their medical record information.

Confidentiality Protections

Identifiable health information will not be reused or disclosed to any other person or entity, except as required by law, for authorized oversight of the research study, or for other permitted research purposes. Research records will be secured in a locked file cabinet in an access-controlled office. Electronic records will be maintained on an Aultman server using identification and secure password. Records containing PHI will be limited in access to the research team only.

Research records will be securely stored in accordance with retention requirements of local and national regulations. The minimum obligations will be six (6) years following study closure. The ICF states that patient records will be stored up to 10 years. After this time records may be destroyed, the method of destruction will be by shredding per institutional policy.

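### The artery-size endpoint is given only a before/after paired t test, so the planned analysis contains no comparison of nitroglycerine with placebo

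*Combined protocol and SAP*

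**What the plan says.** The Hypothesis opens with artery size: "Transdermal vasodilators will increase radial artery size and reduce radial artery spasm". Under End Points, the first secondary endpoint is the within-patient change in area: "Change in ipsilateral radial artery cross sectional area (mm²) before application of topical nitroglycerine / placebo (pre-dilation) vs. prior to arterial puncture". The Study Design section describes a double-blind, placebo-controlled comparison, and Methods item 2 has patients "randomized 1:1 to control arm (40 mg Lidocaine + placebo) or study arm (40 mg lidocaine + 30 mg nitroglycerine".

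The only analysis given for artery size is in Statistical Analysis: "The radial artery dimensions before and after application of the study drug or placebo will be compared using paired sample t test". The section does not say whether the test is run by arm or pooled. It names no between-arm test, estimate or confidence interval for this endpoint.

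The primary endpoint is handled differently in the same section: "Relationship between use of nitroglycerine and radial spasm will be analyzed using Pearson Chi Square test". Procedural failure also gets a chi-square test, and the discomfort score and post-procedure pulse each get a Mann-Whitney test. All of these compare two independent groups.

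**The concern.** A before/after test asks whether the artery changed. The trial asks whether it changed more with nitroglycerine than with placebo. These differ whenever something other than nitroglycerine can move the measurement, and the document gives reasons why it might:

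- Both arms receive 40 mg of topical lidocaine (Methods item 2).
- Both wait at least 60 minutes between application and the procedure (Methods item 7).
- The second scan is taken in the Cath Lab (Methods item 14). For outpatients, the preparation is applied in the Ambulatory Cardiac Unit, and the first scan comes before application. The setting therefore changes as well as the time.

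A shift common to both arms could then be credited to nitroglycerine. Conversely, if both arms change significantly, the plan offers no way to say whether nitroglycerine did more. Artery size is the mechanism by which the topical drug is supposed to reduce spasm, so the missing contrast also weakens the interpretation of the primary result.

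**Working it through.** **Is there a treatment contrast anywhere?** The document's efficacy endpoints and planned tests are:

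| Endpoint | Planned test | Compares arms? |
|---|---|---|
| Spasm (primary) | Pearson chi-square | Yes |
| Change in artery area | Paired t test, before vs after | No |
| Procedural failure | Pearson chi-square | Yes |
| Forearm discomfort (VAS) | Mann-Whitney | Yes |
| Post-procedure pulse | Mann-Whitney | Yes |

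Artery area is the only one without a two-group test.

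**What the paired test estimates.** Let c be the mean change common to both arms and δ the extra change due to nitroglycerine.

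- Nitroglycerine arm alone: the paired test estimates c + δ.
- Placebo arm alone: it estimates c.
- Both arms pooled at 1:1: it estimates c + δ/2.

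None of these is δ. With δ = 0 and c > 0, both the nitroglycerine-arm test and the pooled test reject increasingly often as the sample grows.

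**Size, with no nitroglycerine effect (δ = 0).** The document states no alpha, sample size, SD or effect size, so there is no planned figure to reproduce. Everything below assumes a two-sided 5% level, normally distributed change, and c in units of the SD of change.

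Simulation, 20,000 trials per setting, c = 0.2:

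| n per arm | Nitroglycerine-arm paired test shows enlargement | Pooled paired test significant | Significant on nitroglycerine only | Two-sample t test on change significant |
|---|---|---|---|---|
| 50 | 28% | 51% | 20% | 5.0% |
| 100 | 50% | 80% | 25% | 5.0% |
| 200 | 80% | 98% | 16% | 5.3% |

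Over n = 50, 100 and 200 and c from 0 to 0.5, the nitroglycerine-arm test shows enlargement in 2.3% to 100% of trials. The two-sample test stays between 4.6% and 5.4%.

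**The arm-by-arm reading in closed form.** If p is the power of each within-arm paired test (noncentral t), the chance of a significant nitroglycerine arm with a non-significant placebo arm is p(1 − p):

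- n = 100, c = 0.20: p = 0.508, so 0.508 × 0.492 = 0.250.
- n = 150, c = 0.15: p = 0.446, so 0.446 × 0.554 = 0.247.
- n = 200, c = 0.10: p = 0.291, so 0.291 × 0.709 = 0.206.

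These settings lie close to the maximum, because p(1 − p) cannot exceed 0.25. Across common shifts:

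| c (SD of change) | 0.10 | 0.20 | 0.30 | 0.40 | 0.50 |
|---|---|---|---|---|---|
| n = 100 | 14% | 25% | 13% | 2.2% | 0.1% |
| n = 200 | 21% | 16% | 1.2% | <0.1% | <0.1% |

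At c = 0, the pattern in the direction favouring nitroglycerine has probability 0.025 × 0.95 = 2.4%. A valid two-sided 5% between-arm test would wrongly favour nitroglycerine 2.5% of the time at every value of c.

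**ANCOVA against a comparison of change scores.** With equal pre and post variances and pre–post correlation r, the variance ratio is (1 − r²) / [2(1 − r)] = (1 + r)/2. That gives 0.75, 0.85 and 0.95 at r = 0.5, 0.7 and 0.9.

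**The case against.** The strongest reply is that this is a secondary, supportive endpoint. The Aim lists spasm, comfort and patency but not artery size, and the Study Design sentence names spasm and procedural success. The Background already treats dilation by transdermal nitroglycerine as established. The primary analysis does compare the arms. The images are collected in both arms, so the gap lies in one sentence of the plan and not in the design or the data. All of that is correct. It limits the consequence, but it does not give the endpoint a valid test.

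The second reply concerns the numbers. Nowhere does the plan say it will declare an effect when one arm is significant and the other is not; that rule is inferred. The document also offers no evidence that the placebo arm shifts, and the error rate of the inferred rule runs from near zero to 25% depending on an unknown shift. This also stands, and the percentages should be read as illustrations. The defect does not depend on them: the paired test does not estimate δ under any assumption.

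Third, a two-sample t test on change would also be valid and matches the endpoint's wording. That is right. ANCOVA is preferred because it is at least as precise under the stated assumption, though the gain is only 5% at r = 0.9.

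**Conclusion.** The concern holds. For artery size, the named test contains no nitroglycerine-versus-placebo contrast, and no other part of the document supplies one. Carrying out the plan exactly would leave the first secondary endpoint, and the opening part of the hypothesis, untested against the randomised control. This is a wrong test for the question, not a missing detail.

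How misleading the result could be depends on any change common to both arms, which is unknown. At an assumed common shift of 0.2 SD and 100 per arm, a pooled paired test would be significant in about 80% of trials with no drug effect. The arm-by-arm reading would falsely favour nitroglycerine in about 25%, which is its worst case. If there were no common shift, neither false-positive rate would be inflated, but there would still be no estimate of the treatment difference. The primary spasm comparison is unaffected.

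**What to change.** Replace the artery-size sentence in Statistical Analysis with a between-arm ANCOVA: post-dilation cross-sectional area as the outcome, treatment arm as the factor and pre-dilation area as the covariate. Report the adjusted mean difference in mm² with its 95% confidence interval. Keep the within-arm before/after changes as descriptive summaries, and state that no treatment effect will be inferred from them. Make the change before unblinded data are examined, so that the choice among post values, change scores and ANCOVA is not left open.

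The cost is one sentence. Both scans are already collected in both arms, and SPSS, the software the plan names, can fit the model.

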6. Pre-procedure ipsilateral radial pulse strength (0-4+) will be documented. (4+ Bounding, 3+ Increased, 2+ Normal, 1+ Weak, 0+ Absent or nonpalpable)
7. Transdermal preparation will be applied to ipsilateral wrist overlying radial pulse (centered approximately 1 inch proximal to radial styloid process) at least 60 minutes before procedure start time at a dose of 40mg (6 ribbons of 2 inches each) of 5% Lidocaine and 30mg (8 ribbons of 2 inches each) of 2% Nitroglycerine/Placebo.
8. Patients will complete the Amsterdam Preoperative Anxiety and Information Scale (APAIS).
9. Vitals signs to be checked every 30 minutes (± 10 minutes) after application of the topical preparation for 60 minutes (± 10 minutes) then every 60 minutes (± 10 minutes) until procedure.
10. If SBP < 100 mm Hg and patient complains of dizziness or light-headedness or if SBP < 90 mm Hg, the topical preparation will be removed promptly, 250 ml of 0.9% Normal Saline (NS) IV bolus will be given over 15 minutes, and provider will be notified immediately.
11. If patient complains of headache, one or two tablets of 500 mg acetaminophen will be given by mouth every 4 hours as needed. One tablet will be given if the patient reports a value of 0-3 on the pain scale, and two tablets will be given if the patient reports a value of 4 or greater on the pain scale. The maximum dose of acetaminophen is 4g in 24 hours.
12. If 30 minutes after acetaminophen administration, headache intensity $\geq 5/10$ or patient unable to tolerate intensity of headache, the topical preparation will be removed promptly and provider will be notified immediately.
13. If any of the safety endpoints occur, an investigator will be notified immediately and further decision to proceed with cardiac catheterization or additional workup or treatment would be at the discretion of the investigator.
14. Immediately prior to sterile preparation of access site, transdermal preparation will be removed in Cath Lab and post-dilation cross sectional image of ipsilateral radial artery (approximately 1 inch proximal to radial styloid process) will be captured using bedside sonogram applying no more than gentle pressure.

15. Conscious sedation with intravenous fentanyl and midazolam given with exact dosing at operator's discretion (based on patient's hemodynamic status and comorbid conditions).

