16. After sterile preparation 0.5 – 1.0 ml of subcutaneous lidocaine is administered and radial artery cannulated using modified seldinger technique with 5F or 6F hydrophilic sheath.
17. Parenteral radial cocktail (IV/IA heparin +/- IA nitroglycerine +/- IA verapamil) is given with exact combination and dose at discretion of operator based on patient's hemodynamic status.
18. Coronary angiogram and or intervention performed adopting best practices with care to minimize procedure time, contrast volume and catheter exchanges and avoiding side branches.
19. Following parameters are documented:
 - a. Patient demographics (Age, Sex, BMI, Race)
 - b. Conscious sedation drugs and doses used
 - c. Sheath size
 - d. Number of arterial sticks before arterial access: One or more (Blood in arteriotomy needle equates arterial stick)
 - e. Wire passage in one or more attempts
 - f. Sheath insertion in one or more attempts
 - g. Radial parenteral cocktail used
 - h. Radial artery spasm score:
 - i. Verbal or nonverbal expression of discomfort in the forearm during catheter/sheath manipulation – Absent:0; Present:1
 - ii. Difficulty in manipulating the catheter – Absent:0; Present:1
 - iii. Difficulty in sheath removal – Absent:0; Present:1
 - iv. Additional use of intraarterial nitroglycerine or verapamil after the initial vasodilator cocktail for suspected radial artery spasm – No:0; Yes:1
 - i. Use of long sheath
 - j. Use of hydrophilic wires or catheters
 - k. Tortuosity of UE vessels / anatomic variants
 - l. Catheters used
 - m. Contrast volume

- n. Difficulty in removing catheters and sheath
- o. Use of IA/IV NTG and/or verapamil at end of procedure for sheath removal: provisional use when radial artery spasm present or suspected vs. routine pre-emptive use to avoid radial artery spasm per operator standard practice.
- p. Length of procedure
- q. Change to femoral arterial access and reason
- r. Procedures performed

20. Patient's perceived peri-procedure forearm discomfort documented using VAS (1-10) at the completion of the procedure

21. Post procedure strength of ipsilateral radial pulse (0-4+) after radial band removal documented and presence and size of hematoma at access site at time of radial band removal documented

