22. For patients who have the sheath left in place for percutaneous coronary intervention (PCI) as a separate procedure at a later time, data will be collected for the initial diagnostic catheterization only. The procedure will be considered completed with removal of last diagnostic catheter. Post procedure pulse will be the radial pulse after the PCI.

23. Patients are monitored for adverse events for the following duration:

- a. For patients discharged home from the ambulatory cardiac unit (same day unit) after procedure completion:
 - i. Until discharged home
- b. For hospitalized patients:
 - i. Until 120 minutes after Radial band, or comparable product, removal

Inclusion criteria:

1. Age: 18 years or older
2. Radial artery catheterization +/- intervention

Exclusion criteria:

1. Hypersensitivity or contraindication to lidocaine
2. Hypersensitivity or contraindication to nitroglycerine
3. Recent use of PDE5 inhibitors (<24 hours after sildenafil or vardenafil; <48 hours after tadalafil)
4. Baseline weak radial pulse (0 or 1+)

5. Baseline hypotension SBP < 100mmHg at the time of enrollment
6. Dizziness or light-headedness at the time of enrollment
7. Severe Aortic Stenosis or HOCM
8. Previous unknown bypass grafts or known LIMA graft
9. Chest pain within 6 hours of IP administration
10. More than 2 episodes of chest pain within 24 hours prior to IP administration
11. Use of sublingual, transdermal, or intravenous nitroglycerine within 6 hours prior to IP administration
12. Likely need for use of nitroglycerine for non-study indication
13. Narcotic or sedative within 4 hours of enrollment
14. Women who are suspected or known to be pregnant or breastfeeding

Processing of cross sectional sonographic images of radial artery:

1. Horizontal diameter
2. Vertical diameter
3. Average diameter
4. Cross Sectional area
5. Presence of atherosclerotic plaque

Data and Safety Monitoring Plan

A data safety monitoring committee will be assigned to review each case for eligibility, adherence to the protocol, occurrence of adverse events, and accuracy of data. This will be completed on a regular basis. The first review will be conducted after enrolling the first 10 patients. Regular reviews will be scheduled at increments of 50 randomized patients until enrollment goals are met. Any deficiencies found during this review will be addressed and reported to necessary parties.

Statistical Analysis

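### The post-procedure pulse test ignores the pulse grade recorded before dosing; using it is an optional, low-cost gain in precision, not a correction of bias

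*Combined protocol and SAP*

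**What the plan says.** The whole analysis plan for this endpoint is one sentence under Statistical Analysis: "The post procedure pulse will be analyzed using Mann Whitney test". It names no adjustment, stratification or change score.

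The baseline is collected. Methods step 6 states: "Pre-procedure ipsilateral radial pulse strength (0-4+) will be documented". The product goes on at step 7, so this grade precedes treatment. Exclusion criterion 4 also depends on it: patients graded 0 or 1+ are not eligible, which leaves 2+, 3+ and 4+ as the possible baseline values. No analysis in the document uses the grade.

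The outcome grade is taken later, at step 21: "Post procedure strength of ipsilateral radial pulse (0-4+) after radial band removal documented". For patients whose sheath stays in for a later intervention, step 22 takes the pulse after that intervention.

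The two scales carry different labels. Step 6 has "4+ Bounding, 3+ Increased, 2+ Normal, 1+ Weak, 0+ Absent or nonpalpable". Secondary endpoint 4 has "2 + suggesting a slightly more diminished pulse than normal; 3 + is a normal pulse".

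**The concern.** Patients enter with different pulses. A test on the post-procedure grades alone leaves whatever part of those differences persists in the comparison as noise. If the two grades are correlated, comparing patients within baseline grade removes part of that noise and raises power without any new data.

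The Aim and Hypothesis both name post-procedure radial artery patency, and among the efficacy endpoints this is the one that bears on it. The document states no sample size or power, so nothing shows that there is precision to spare.

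**Working it through.** There is no planned figure to reproduce, because the document gives no sample size, significance level, effect size, grade distribution or correlation for this endpoint. Everything below is illustrative.

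**From the documents:** a five-level ordinal outcome (0 to 4+); baseline limited to 2+, 3+ and 4+; allocation 1:1 (Methods step 2).

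**Assumed:** two-sided 5% level; 100 patients per arm; post-procedure grades 0 to 4+ in the control arm distributed 5/15/50/25/5%; treatment shift 0.35 SD on a latent normal scale; latent baseline-to-post correlation 0 to 0.7; three splits of baseline grade.

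*Step 1, closed-form guide.* Adjusting for a baseline whose observed correlation with the outcome is r multiplies the variance by 1 − r². If the unadjusted test has 80% power, the adjusted power is Φ[(1.960 + 0.842)/√(1 − r²) − 1.960]:

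- r = 0.1: variance × 0.99, power 80.4%
- r = 0.3: variance × 0.91, power 83.6%
- r = 0.5: variance × 0.75, power 89.9%
- r = 0.7: variance × 0.51, power 97.5%

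Here r is the correlation between the recorded grades. Grouping into three levels makes it lower than the latent correlation used in step 2.

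*Step 2, simulation on the ordinal scale.* The stratified statistic is Z = Σ wₖ[Rₖ − n₁ₖ(nₖ + 1)/2] / √Σ wₖ²Vₖ over baseline grades k. Rₖ is the rank sum of the active arm within grade k, wₖ = 1/(nₖ + 1), and Vₖ is the tie-corrected permutation variance of Rₖ. With a single stratum this is the ordinary Mann-Whitney test. Power over 3,000 simulated trials per setting, unstratified then stratified:

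| Baseline split 2+/3+/4+ | Latent corr. 0 | 0.3 | 0.5 | 0.7 |
|---|---|---|---|---|
| 40/40/20% | 0.61, 0.60 | 0.63, 0.65 | 0.62, 0.70 | 0.62, 0.80 |
| 70/25/5% | 0.61, 0.61 | 0.63, 0.65 | 0.62, 0.69 | 0.61, 0.75 |
| 90/8/2% | 0.64, 0.63 | 0.62, 0.64 | 0.62, 0.66 | 0.63, 0.70 |

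In power points, the gains across each row are −1, 2, 8, 18; then 0, 2, 7, 14; then −1, 2, 4, 7. The simulation standard error of one power figure is about √(0.62 × 0.38/3000) = 0.009, so gains of 1 or 2 points are close to noise.

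*Step 3, sensitivity to the shift.* With a shift of 0.43 SD, which puts the unstratified test at about 79 to 82% power, the largest gain is 0.926 − 0.796 = 0.13 (latent correlation 0.7, split 40/40/20%).

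*Step 4, validity.* With no treatment effect, both tests rejected in 4.2 to 5.5% of trials at the 0.35 SD settings. The planned test keeps its level.

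*Step 5, effect of the label conflict.* If half of the patients were graded one step higher at baseline because graders mixed the two sets of labels, the gain at latent correlation 0.7 falls from about 14 to 18 points to about 8 to 10 (splits 70/25/5% and 40/40/20%).

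**The case against.** The strongest case for leaving the sentence alone is that the planned test is simple and valid, that this is the last of four secondary endpoints, and that there is no stated power target to miss. The benefit could also be trivial. Step 6 calls 2+ normal and the exclusion removes everything below it, so most patients may share one grade. Between the two gradings come cannulation with a 5F or 6F sheath, vasodilators at the operator's discretion, band removal and, for some patients, a later intervention. Any of these could weaken the correlation. All of this stands, and it limits both the size and the priority of the point. It does not remove it, because the stratified test costs about 1 power point at worst in these settings.

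A reader might infer more than the documents support:

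- **That the planned comparison is biased, or that chance imbalance in baseline pulse is a second defect.** The plan says "patients without any exclusion criteria will be randomized 1:1 to control arm". Under that allocation, chance imbalance is already part of the test's null distribution. It is the same lost precision described in another way.
- **That the baseline grade must be the best predictor of the later one.** Nothing in the document says so. The Background names a different influence on post-procedure flow, the ratio of artery to sheath size.
- **That the gain is large.** A latent correlation of 0.85 can take power from 0.68 to 0.92 in a similar simulation, but no passage supports a correlation that high.
- **That the gain is entirely free.** The label conflict can erode it, as step 5 shows.

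**Conclusion.** The point holds as a matter of efficiency. The analysis of secondary endpoint 4 leaves out a pre-treatment measurement of the same quantity that is scheduled for every patient. The planned Mann-Whitney test is valid and its result would be interpretable.

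Under the stated assumptions, stratifying changes power by between about −1 point and +18 points. The gain vanishes as the correlation approaches zero or as all patients fall into one baseline grade. It reaches the top of the range only with a latent correlation of 0.7 and baseline grades spread 40/40/20%. Where the trial would lie in that range cannot be learned from the documents.

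This is an optional, low-cost improvement to one secondary endpoint.

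**What to change.** Replace the sentence on post-procedure pulse with:

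> The post-procedure pulse will be compared between arms with a Mann-Whitney test stratified by pre-procedure pulse grade (van Elteren test); the unstratified Mann-Whitney test will be reported as a sensitivity analysis.

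Name this one method, with no alternative model left open, and do so before unblinding, so that the adjustment cannot look data-driven. State in advance how a sparse baseline grade will be pooled, since a stratum with patients in only one arm contributes nothing. Confirm that the named software can run the stratified test.

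Reconcile the pulse labels in Methods step 6 and secondary endpoint 4 so that graders use one scale. The stratified test does not need the baseline and outcome labels to match, because baseline enters only as a stratum. It does need all graders to apply the same labels at baseline. A change score would not be interpretable while the two scales differ.

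The cost is one sentence in the analysis section and one harmonised scale. No new data are needed.
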